14.0 STATISTICAL CONSIDERATIONS

14.1 Study Design/Primary Endpoint

The study is a randomized phase III design, and the primary endpoint in both treatment arms is median PFS. PFS will be defined as the time from randomization day until objective progression or death from any cause. The PFS distributions of the two treatment arms will be estimated by Kaplan-Meier survival analysis and the PFS distributions will be compared by an unstratified log-rank test. Ninety-five percent confidence intervals for the Kaplan-Meier PFS estimates will be calculated using

Greenwood's formulae. The primary comparison will be made using the intent-to-treat (ITT) patient population. Patients will be analyzed based on their randomization assignments, regardless of therapy initiation or compliance. A secondary analysis will be performed comparing "evaluable" patients as patients who met eligibility requirements, have initiated therapy, and were not removed from the study for non-compliance or patient withdrawal.

The median PFS for MM patients receiving Revlimid /dexamethasone chemotherapy (Rd) (Arm A) is expected to be approximately 25.5 months, as reported in the MM-010 study of continuous Rd vs Rd for 18 months (Facon T, Dimopoulos M, Dispenzieri A, et al: Initial phase 3 results of the FIRST trial in newly diagnosed multiple myeloma patients ineligible for stem cell transplant. 2013 ASH Annual Meeting. Abstract 2. Presented December 8, 2013.). Therefore, the target median PFS for patients receiving Revlimid/dexamethasone/Clarithromycin (BiRd) (Arm B) is hypothesized to be 44.6 months (target hazard ratio = 1.75).

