14.3 Analysis of Progression-Free Survival

Because the analysis of PFS can be difficult, especially in the presence of missing data and lost-to-follow-up, sensitivity analyses can be helpful in determining whether the PFS analysis is robust. As suggested by the alternative PFS definitions recommended in the FDA's Guidance for Industry, "Clinical Trial Endpoints for the Approval of Cancer Drugs and Biologics (May, 2007), the following three types of PFS analyses will be

conducted:

Table A. PFS #1 (includes documented progression only) (Primary PFS Analysis):

Situation	Date of Progression or Censoring	Outcome
No baseline tumor assessments	Randomization	Censored
Progression documented between scheduled visits	Earliest of: 
 • Date of hematological assessment showing progression; or • Date of radiological assessment showing progression; or • Date of urine assessment showing progression 	Progressed
No progression	Date of last hematological, radiological, or urine assessment	Censored
Treatment discontinuation for undocumented progression	Date of last hematological, radiological, or urine assessment	Censored
Treatment discontinuation for toxicity or other reason	Date of last hematological, radiological, or urine assessment	Censored
New anticancer treatment started	Date of last hematological, radiological, or urine assessment	Censored
Death before first PD assessment	Date of death	Progressed
Death between adequate assessment visits	Date of death	Progressed
Death or progression after more than one missed visit	If progression: 
 • Date of hematological assessment showing progression; or • Date of radiological assessment showing progression; or • Date of urine assessment showing progression OR, if not progression: Date of last hematological, radiological, or urine assessment	Censored

Table A represents the primary PFS analysis that only includes well-documented and verifiable progression events. Other data are censored. In Table A, the progression dates are 1) based only on radiological assessments verified by an IRC (clinical progression will not be considered a progression endpoint), 2) assigned to the first time when disease progression is noted, and 3) the date of death when the patient is closely followed. However, deaths occurring after two or missed visits will be censored at the last visit.

Table B. PFS #2 (uniform progression and assessment dates) (PFS Sensitivity Analysis #1):

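### Table A, the primary PFS analysis, censors documented progressions and deaths after more than one missed visit, although section 14.1 counts both as events

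*Combined protocol and SAP*

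**What the plan says.** Section 14.1 states the endpoint without qualification: "PFS will be defined as the time from randomization day until objective progression or death from any cause". The primary test is an unstratified log-rank test in the ITT population.

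Section 14.3 (Analysis of Progression-Free Survival) then sets out three sets of coding rules and labels Table A the primary one. Its last row covers "Death or progression after more than one missed visit". The date cell has two branches. A progression takes the date of the assessment that showed it, for example "Date of hematological assessment showing progression"; otherwise the date of the last assessment applies. The outcome cell has one entry for both branches: censored. The paragraph below Table A repeats the rule for deaths only: "However, deaths occurring after two or missed visits will be censored at the last visit".

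The text after Table C says that all three tables initially censor patients who died or progressed after more than one missed visit. It adds that the analyses will also be repeated with these patients as events, dated at death. Table C's last row, however, covers deaths only.

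**The concern.** Two passages define the primary endpoint, and they disagree about the same patients. Followed literally, Table A removes events that 14.1 counts, and two analysts could code one patient differently. The plan does not say which rule counts toward the 66 events for the futility look or the 133 for the final analysis.

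If affected events are equally common in both arms, the trial loses events or time. If they are not, the hazard ratio moves in favour of the arm with more of them. The trial is open-label and one arm takes an extra daily drug, so equality cannot simply be assumed.

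**Working it through.** **The rules side by side**, for three patients whose event follows more than one missed visit:

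| Patient | 14.1 | Table A | Table B | Table C | Re-run |
|---|---|---|---|---|---|
| Documented progression, alive | Event at progression | Censored on the progression date | Censored at last adequate visit | No row censors it | Event, but no date exists |
| Documented progression, later death | Event at progression | Censored on the progression date | Censored at last adequate visit | No row censors it | Event at death (late) |
| Death, no progression | Event at death | Censored at last assessment | Censored at last adequate visit | Censored at last adequate visit | Event at death (agrees with 14.1) |

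**Inputs from 14.1 and 14.2.** Medians 25.5 and 44.6 months, hazard ratio (control over experimental) 1.75, two-sided 0.05, 90% power, 133 events, 153 patients per arm, 36 months of accrual, data at month 48.

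**The plan's own figure.** Schoenfeld: 4 × (1.960 + 1.282)² / (ln 1.75)² = 134.2, against 133 stated. Power at 133 events: Φ(√(133/4) × ln 1.75 − 1.960) = Φ(3.227 − 1.960) = 0.897. The event target is sound.

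**Model.** Let q be the share of an arm's true events that falls in the last row. The documents give no value, so every q below is an assumption. With censoring at the event date, the counted hazard is (1 − q) times the true hazard, so

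observed HR = true HR × (1 − q_Rd) / (1 − q_BiRd).

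**Equal shares, 10% and 10%.** The ratio is 1, so there is no bias.
- Starting from 133 true events: 133 × 0.90 = 119.7 counted, power 0.865.
- At a month-48 cut: expected events are 153 × 0.540 + 153 × 0.364 = 138.3, and 138.3 × 0.90 = 124.5 are counted. Simulated power is about 0.87.
- Waiting for 133 counted events: 133 / 0.90 = 147.8 true events are needed and power stays at 0.897. With 306 patients this takes until about month 51 instead of about month 46.5.

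**Unequal shares**, at 133 counted events. The shift in the test statistic is √(133/4) × ln(observed HR).

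| Rd / BiRd share | True HR | Observed HR | Result |
|---|---|---|---|
| 1% / 3% | 1.00 | 0.99/0.97 = 1.02 | Shift 0.118; 1 − Φ(1.960 − 0.118) = 3.3% false significance for BiRd |
| 5% / 15% | 1.00 | 0.95/0.85 = 1.118 | Shift 0.641; 1 − Φ(1.960 − 0.641) = 9.4% |
| 15% / 5% | 1.75 | 1.75 × 0.85/0.95 = 1.566 | Power 0.734 |

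Log-rank simulation at month 48 agrees: about 3% to 3.5% in the first case, about 10% in the second, and power about 0.70 in the third. If the 5% / 15% cases are wholly or half deaths censored 2.8 to 6 months early, the hazard ratio is 1.11 and false significance 9% to 10%.

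**The re-run**, no true effect, shares 5% / 15%, assumed median survival after progression 24 months, event at death if before month 48 and otherwise censored at the data cut:

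| Last-row cases | HR | False significance for BiRd |
|---|---|---|
| All progressors | 1.11 | about 9% |
| Half progressors, half deaths | 1.05 | about 4.5% |
| All deaths | 1.00 | nominal, about 2.5% |

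About 61% to 63% of these progressors are alive at month 48 and so have no event date in the re-run.

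**The case against.** The strongest reply is that the progression half is a slip and the death half a legitimate choice. The text around Table A says it keeps well-documented progressions, dates them when first noted, and names only deaths as censored after missed visits. The two-branch date cell makes most sense if the branches were meant to end differently. The sentence that says progressors are censored too is wrong about Table C, so it is weak evidence of intent. All this stands as to intent. It does not make the row usable, since an analyst must still depart from the outcome cell to code a progression as an event.

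Censoring deaths after missed visits is a recognised convention, and the section attributes its PFS definitions to regulatory guidance. That stands. It makes the death half a conflict to reconcile with 14.1, not an error of method.

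A reader might infer that nothing in the plan recovers these events. The documents do not support that: the re-run follows 14.1 for deaths without progression, and Table C has no row that censors progressions after missed visits.

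A reader might also infer that the primary result will favour BiRd. Nothing in the documents shows this. Both arms share one visit schedule. Section 9.5 removes a patient whose cycle is delayed by more than 4 weeks, which limits long gaps on treatment. Section 10.4 plans monthly to bi-monthly clinic follow-up after discontinuation, with 6-monthly contact only for those who decline it. The direction and size of any imbalance are unknown.

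Nor does the ITT sentence, "Patients will be analyzed based on their randomization assignments, regardless of therapy initiation or compliance", settle the matter. It governs which arm a patient is analysed in, not how an event is coded.

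**Conclusion.** The conflict is real and should be fixed. The last row of Table A contradicts 14.1. Its progression half is wrong on any reading, because it censors a documented progression on its own date; its death half is a defensible convention that the endpoint definition does not mention. The re-run cures neither half of the primary analysis, and it handles progressors badly.

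The effect cannot be sized from the documents. It ranges from no bias with equal shares, through a hazard ratio of 1.02 at 1% / 3%, to 1.12 and about 10% false significance at 5% / 15%. All shares, and the 24-month survival after progression, are assumptions. The power loss with equal shares applies to a fixed month-48 cut and disappears if the trial waits for 133 counted events. The sample-size arithmetic is not in question.

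Three nearby items need separate reconciling and carry no weight here: the pointer to 14.2 for the primary analysis; the unstated precedence of the rows "Treatment discontinuation for toxicity or other reason" and "New anticancer treatment started" over later events; and the text that progression dates are "based only on radiological assessments verified by an IRC", although the table accepts hematological and urine dates.

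**What to change.** 1. Split Table A's last row in two. Code a documented progression as progressed, at the date of the assessment that showed it.
2. For a death without earlier progression, make 14.1 and Table A agree. The default is what 14.1 already states: an event at the date of death. Keep missed-visit censoring as a named sensitivity analysis, and say for it what a missed visit is on and off treatment. If the sponsor prefers that censoring as primary, 14.1 must say so.
3. State that the same rule counts toward the 66 and 133 events.
4. In the re-run, use the progression date, and the date of death only if no progression was recorded. Correct its description of Table C.

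The cost is text edits, with no change in sample size. The downside is that a progression first seen after a gap is dated late, and more often so in an arm with more gaps. The retained sensitivity analysis and the by-arm comparison of follow-up already planned in 14.3 will show how much this matters.

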10.11 Criteria for removal from study

Rules for termination of the study for the individual subject are listed below:

- Subjects may withdraw consent and stop participation at any time.
- Any Grade 4 skin toxicity (i.e. Stevens Johnson syndrome) or Grade 4 hypersensitivity (i.e. anaphylaxis).
- Progression of multiple myeloma, as defined by the International Myeloma Working Group Criteria (Appendix 1 of the protocol).
- Development of any co-morbid condition or excessive toxicity that would make further participation in the protocol unsafe.
- The development of any comorbid condition of excessive toxicity that would make further participation in the protocol unsafe.
- Non-compliance or refusal of the patient to continue treatment and/or evaluation.
- Major violation of the study protocol.
- Any adverse event(s) that, in the judgment of an Investigator, may cause severe or permanent harm if the study medications are continued.
- At the discretion of the principal investigator and/or Celgene Pharmaceuticals, Inc. for any reason.
- Loss to follow up.
- Death of patient

Any possible premature discontinuation would be documented adequately with reasons being stated, and information would have to be issued according to local requirements (e.g., IRB/EC, regulatory authorities, etc.).

10.11.2 The responsible Clinical Investigator as well as Celgene Pharmaceuticals, Inc. have the right to discontinue this study at any time for reasonable medical or administrative reasons in any single center. Possible reasons for termination of the study could be but are not limited to:

- Unsatisfactory enrollment with respect to quantity or quality.
- Inaccurate or incomplete data collection.
- Falsification of records.
- Failure to adhere to the study protocol.

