
  ≥50% reduction in the level of the serum monoclonal paraprotein.  Reduction in 24h urinary light chain excretion either by ≥90% or to <200mg.  For patients with light chain only disease, then a 50% reduction in the difference between the involved and unininvolved free light chain level may be substituted for the M-protein measurement.  For patients with non-secretory myeloma only, ≥50% reduction in plasma cells in a bone marrow aspirate and on trephine bone biopsy, if biopsy is performed.  ≥50% reduction in the size of soft tissue plasmacytomas (by radiography or clinical examination).  No increase in size or number of lytic bone lesion (development of a compression fracture does not exclude response)
Stable Disease (SD) requires the following:

  Not meeting the criteria stringent complete response (sCR), complete response (CR), very good partial response (VGPR), or partial response (PR)
Plateau:

  Stable values (within 25% above or below value at the time response is addressed) 
Patients in which no significant change (<50% decrease or <25% increase from baseline) in the production rate of the monoclonal serum protein or Bence-Jones protein excretion and no new lytic lesions and/or plasmacytomas are detected.

Relapse from CR requires at least one of the following:

- Reappearance of serum or urinary paraprotein on immunofixation or routine electrophoresis, confirmed by at least one further investigation and excluding oligoclonal immune reconstitution.
- ≥5% plasma in a bone marrow aspirate or trephine bone biopsy.
- Development of new lytic lesions of soft tissue plasmacytomas or definite increase in the size of residual bone lesions (development of a compression fracture does not exclude continued response and may not indicate progression).
- Development of hypercalcemia (corrected serum calcium >11.5mg/dl or 2.8 mmol/l) not attributable to any other cause.

Progressive disease (PD) for patients not in CR requires one or more of the following:

- >25 increase in the level of the serum monoclonal paraprotein, which must also be an absolute increase of at least 5g/L and confirmed by at least one repeated investigation.

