- >25 increase in the 24h urinary light chain excretion, which must also be an absolute increase of at least 200mg/24h and confirmed by at least one repeated investigation.
- >25% increase in plasma cells in a bone marrow aspirate and on trephine bone biopsy, which must also be an absolute increase of at least 10%.
- Definite increase in the size of existing bone lesions or soft tissue plasmacytomas.
- Development of new bone lesions or soft tissue plasmacytomas (development of a compression fracture does not exclude continued response and may not indicate progression).
- Development of hypercalcemia (corrected serum calcium >11.5mg/dl or 2.8 mmol/l) not attributable to any other cause.

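### The text under Table A limits primary PFS progression to IRC-verified imaging, contradicting Table A's own rows and Appendix I

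*Combined protocol and SAP*

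**What the plan says.** Section 14.3 (Analysis of Progression-Free Survival) gives two rules for the same analysis.

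- **Table A, row for documented progression.** The date is the earliest of three alternatives. One is "Date of hematological assessment showing progression; or", another is "Date of urine assessment showing progression", and the third is the corresponding radiological date. The censoring rows also use the last assessment of any of these three types.
- **Paragraph under Table A.** It opens "Table A represents the primary PFS analysis that only includes well-documented and verifiable progression events" and then says that the progression dates in the table are "based only on radiological assessments verified by an IRC (clinical progression will not be considered a progression endpoint".

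Section 10.11 takes a patient off study for "Progression of multiple myeloma, as defined by the International Myeloma Working Group Criteria (Appendix 1 of the protocol". In Appendix I, one criterion is enough for progressive disease. Two of the criteria are a confirmed "increase in the level of the serum monoclonal paraprotein" (at least 5 g/L absolute) and a confirmed "increase in the 24h urinary light chain excretion" (at least 200 mg per 24 h absolute). For a patient in complete response, confirmed reappearance of paraprotein alone counts as relapse.

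The Schedule of Assessments (1.3) and section 10.3 have serum and urine protein studies on Day 1 of every cycle. After screening, imaging is done only to confirm remission or progression, or when clinically indicated. No IRC is described anywhere else.

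**The concern.** A restriction to radiology alone cannot be squared with a row that accepts any of three assessment types. In this trial the two rules can classify the same patient differently, because the tests done every cycle are the serum and urine tests and scans are occasional.

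Take a patient whose confirmed M-protein rise meets Appendix I while imaging shows nothing new. Under Table A's row this is an event on the date of the blood or urine result. Under the paragraph it is not an event. Section 10.11 takes the patient off study, and Table A's row for stopping because of toxicity or any other reason, or its row for starting new anticancer therapy, could then censor the patient at the last assessment. That censoring is informative, because progression itself triggers it.

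The futility look at 66 events and the final analysis at 133 events (14.2) would also count different events under the two rules. The trial is open-label, so the choice between them should not wait until data can be seen.

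**Working it through.** **1. Can another part of the plan resolve it?**

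- 14.1 defines PFS by objective progression or death, which fits both rules.
- The closing paragraphs of 14.3 speak of using the progression times as actually reported. That concerns dating, not which assessments count.
- The same paragraphs refer the reader to the first two paragraphs of 14.2 for the primary analysis. Those deal with sample size, apart from a remark that the analysis will be nonparametric.
- 10.11 and Appendix I support Table A's row, but neither is an analysis rule.

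So the contradiction stands.

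**2. Reproducing the design.** Inputs from 14.1 and 14.2: medians 25.5 and 44.6 months, hazard ratio 1.75, two-sided alpha 0.05, 133 events, 153 patients per arm, 36 months of accrual, 48 months in total, no dropout.

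- Power = Φ(√D/2 × ln 1.75 − 1.96). With D = 133: 11.533/2 × 0.5596 − 1.96 = 1.267, so power is 89.7%, against 90% stated.
- With λ = ln 2/median, the probability of an event by month 48 is 1 − (e^(−12λ) − e^(−48λ))/(36λ). This is 0.5397 for Rd and 0.3644 for BiRd. Expected events are 153 × (0.5397 + 0.3644) = 138.3, so 133 is reachable.

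The design figures hold. What is unsettled is which events they count.

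**3. Illustration if the radiology sentence governed.** Let p be the share of PFS events, deaths included, that still counts. The documents give no value; 90%, 80% and, as an extreme, 50% are assumptions. The hazard ratio of 1.75 is assumed to hold for the counted events.

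*Final analysis held when 133 events have occurred under Table A's rows* (D = 133p):

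| p | Counted events | Power |
|---|---|---|
| 100% | 133 | 89.7% |
| 90% | 119.7 | 86.5% |
| 80% | 106.4 | 82.3% |
| 50% | 66.5 | 62.6% |

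*Or waiting for 133 counted events.* Power stays near 90%, but 133/p events under Table A's rows must accumulate: 133/0.9 = 147.8 or 133/0.8 = 166.3. For t > 36, expected events by month t are 153 × Σ[1 − (e^(−λ(t−36)) − e^(−λt))/(36λ)], summed over the two arms. The 133rd counted event moves from about month 46.5 to about month 51 (90%) or 57 (80%).

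These months assume uniform accrual of 306 patients over 36 months, that is 306/36 = 8.5 per month. Section 14.2 says about 9 per month and section 4.2 says 10-15. With all events counted, the 133rd falls at month 45.3, 43.4 or 37.9 for 9, 10 or 15 per month.

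**4. Kaplan-Meier medians.** Suppose uncounted progressions are a constant share of the hazard and are censored when they occur. The expected BiRd curve at month 48 is then 0.5^(48p/44.6): 0.51, 0.55 or 0.69 for p = 90%, 80% or 50%, against 0.47 when all events count. The curve is biased upward, and at a 48-month cut-off the BiRd median would be expected to be not reached.

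**The case against.** The best defence is that the radiology sentence is a stray phrase. Table A's progression row and several of its censoring rows name all three assessment types, 10.11 points to Appendix I, and the same paragraph assigns progression to the first time it is noted. An analyst would probably follow the rows. This stands as a judgement of what was meant. It does not remove a sentence that describes the primary analysis and says the opposite.

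A second defence is that the loss could be partial. Footnote 8 of the Schedule of Assessments provides imaging to confirm progression, and disease status is followed after discontinuation (4.1, 10.4). Deaths, and any later radiological progression that is captured, could still count. This also stands in part, but a scan need not show progression when only M-protein has risen, and nothing guarantees a later one.

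Third, the timing depends on accrual. At 10 patients per month with a 90% share, month 48 still yields 133.5 counted events, so holding that date would cost no power against the 133-event target. That is correct, and the months above are illustrative only.

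A reader might infer more than the documents support:

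- **That one arm is favoured.** Nothing suggests that the counted share differs by arm. With equal shares the hazard ratio is unchanged.
- **That the trial loses power and is also delayed.** These are alternatives, depending on whether the analysis is held or waits.
- **That particular inflated medians would be reported.** Dividing the planned medians by the counted share gives BiRd values beyond 48 months, which a 48-month cut-off cannot show.
- **That the row "Treatment discontinuation for undocumented progression" censors these patients.** A confirmed M-protein rise is documented, so that row does not fit. Only the two rows named above could apply, and then by interpretation.

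**Conclusion.** The plan is wrong as written and must be corrected. The paragraph under Table A contradicts the table it describes and Appendix I, and no other text resolves which rule defines the primary event. The contradiction itself rests on the wording alone and needs no assumption.

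The consequences are conditional on the radiology sentence being followed, which is the less likely reading. Their size depends on a counted share that the documents do not give. Power would be about 86.5%, 82% or 63% at shares of 90%, 80% or 50% if the analysis is held at 133 Table A events; otherwise power stays near 90% with longer follow-up. The stated sample size and event count are not shown to be wrong.

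**What to change.** **Required.** Delete the radiology-only restriction under Table A. Date progression at the earliest hematological, radiological or urine assessment that meets the Appendix I criteria, as the table's row already does. State whether independent review applies and, if it does, that it covers serum and urine data as well as imaging.

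**Minor text corrections in the same section.**

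- Table A's last row gives a progression date but the outcome is censored. Make the two cells agree. The closing paragraphs of 14.3 and Table B show that the initial censoring after missed visits is deliberate.
- The planned re-run of those missed-visit cases uses the date of death throughout, which does not exist for patients who progressed and are alive. Use the documented progression date for patients who progressed, and the date of death only for those who died.
- Change the pointer for the primary analysis from 14.2 to 14.1 and the corrected Table A.

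A further ITT sensitivity analysis ignoring discontinuation, new therapy and missed visits would be a matter of preference and is not required here.

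**Cost.** Wording only: serum and urine protein are already measured every cycle. If independent review is kept, extending it to those results adds some review work.
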